## 4.2 Selection of Study Population

Normal healthy full term infants ( $\geq 37$  weeks gestational age) will be recruited. Subjects will be recruited without regard to race, gender, or ethnicity. Up to 150 subjects will be recruited from established patient populations at CCHMC. These include our CCHMC Pediatric Primary Care Clinic, employees at CCHMC, and our CCHMC study database. Parental permission /informed consent will be obtained from the parents/legal guardians before any procedures are performed. Their parents/legal guardians will be interviewed to assure that the infants meet all the eligibility criteria and will be available for the duration of the study.

Geographically, our proposed study population will be from our primary service area at CCHMC. We do not anticipate targeted recruitment based on minority status, but no minority will be excluded from the study.

## 4.3 Inclusion and Exclusion Criteria

### Subject Inclusion Criteria

Infants who meet the following criteria will be eligible to participate in this study:

1. healthy infant 6 to 13 weeks (12 weeks and 6 days) of age at day of rotavirus vaccine administration
2. free of obvious health problems as established by medical history and confirmed with infant's primary physician prior to Visit 1
3. parent/legal guardian willing to have infant feed from a bottle for contrast
4. parent/legal guardian willing and capable of signing informed consent
5. parent/legal guardian and infant expected to be available for entire study
6. parent/legal guardian can be reached by telephone
7. parent/legal guardian expresses willingness to complete study procedures and receive 2 month immunizations, according to recommended schedule

### Subject Exclusion Criteria

Infants will not be eligible if any of the below conditions apply:

1. gestational age of <37 weeks
2. infant unable to fast for 4 hours prior to MRI procedure
3. receipt of any vaccine except initial HBV (must have at least 28 days between HBV and Visit 1 to be included)
4. history of severe allergic reaction to HBV vaccine
5. contraindications for any of the routine vaccines
  - a. Severe Combined Immune Deficiency
  - b. history of intussusception
6. precautions for either RV1 or RV5 (may interfere with study outcomes)
  - a. altered immunocompetence
    - i. infants with primary and acquired immunodeficiency states, cellular immunodeficiency, hypogammaglobulinemic and dysgammaglobulinemic states
    - ii. infants with blood dyscrasias, leukemia, lymphomas, or other malignant neoplasms affecting the bone marrow or lymphatic system
    - iii. infants on immunosuppressive therapy (including high-dose systemic corticosteroids)
    - iv. infants who are HIV-exposed or infected
  - b. acute gastroenteritis
  - c. moderate or severe acute illness with or without fever
  - d. pre-existing chronic gastrointestinal diseases (e.g., congenital malabsorption syndromes, Hirschsprung's disease, or short-gut syndrome)
  - e. infants with spina bifida or bladder exstrophy (latex rubber is contained in the RV1 oral applicator)
7. sensitivity to latex (latex rubber is contained in the RV1 oral applicator)
8. febrile illness within previous 14 days (axillary temperature of 100.4° F or higher)
9. history of vomiting (forceful expulsion of partially digested milk/food) within 24 hours prior to Visit 1 and/or diarrhea (3 watery stools) within 14 days of Visit 1
10. receipt of any steroids, immunoglobulins, other blood products/transfusion
11. receipt of non-steroidal anti-inflammatory drugs in previous 72 hours (may affect cytokine response)
12. receipt of an antipyretic medication (acetaminophen or ibuprofen) within 72 hours prior to the first dose of rotavirus vaccine or is already planning to administer a prophylactic antipyretic medication on the day of and the day following vaccination (this exclusion does not apply if the caretaker indicates he/she might administer antipyretics after vaccination to reduce a fever)
13. is enrolled or plans to enroll in another clinical trial while participating in this study (observational studies are allowed)
14. any condition which, in the opinion of the investigators, may post a health risk to the subject or interfere with the MRI or vaccine evaluation

15. currently receiving medication for gastroesophageal reflux (GERD) or any other gastrointestinal condition including colic
16. infant who is a relative of any research study personnel
17. allergy to barium
18. failed newborn hearing screening

#### **4.4 Randomization and Study Withdrawal**

##### **Randomization Procedures**

The randomization code will be prepared by statisticians in the Epidemiology and Biostatistics Core at CCHMC. The randomization code will link to the vaccine assignment. The subject will be assigned a randomization code. Randomization will take place prior to the vaccine administration, but after the parent/legal guardian has given permission/informed consent, signed the IRB-approved consent form and met all of the inclusion and none of the exclusion criteria. Infants will be randomized 1:1:1:1 to one of four groups: 1) RV1 alone, 2) RV5 alone, 3) RV1 with routine immunizations (DTaP, Hib, PCV13, HBV and IPV or 4) RV5 with routine immunizations.

##### **Reasons for Withdrawal**

The study personnel may withdraw a subject from the study at any time for the following reasons:

1. unable to comply with the study protocol
2. receipt of blood or blood products (including immunoglobulin) during the study period
3. malignancy or confirmed or suspected immunodeficiency such as HIV infection or severe combined immunodeficiency
4. receipt of or history of any medications or treatments that affect the immune system, such as immune globulin, interferon, immunomodulators, cytotoxic drugs, or other drugs known to be frequently associated with significant major organ toxicity since enrollment
5. receipt of long-term ( $\geq 2$  weeks) potentially immunosuppressive corticosteroid medication during the study period
6. parent/legal guardian request
7. infants who vomit within 15 minutes of rotavirus vaccination will not be withdrawn but will be replaced for analysis purposes
8. allergic reaction to barium

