##### **Handling of Withdrawals**

Every effort will be made to undertake protocol-specific safety follow-up procedures for subjects who are withdrawn by their parents/legal guardians. The subject's parents/legal guardians will be encouraged to participate in the final follow-up contact to occur 14 days after the initial visit.

Subjects who are withdrawn may be replaced if deemed necessary by the study team to meet study enrollment goals.

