## 6.8 Reactogenicity Assessment

Reactogenicity will be assessed for both groups for fourteen days after vaccine receipt (Days 0-14) and recorded by the parent/legal guardian on a provided memory aid. The events will include fever, fussiness and gastrointestinal symptoms such as vomiting and diarrhea (number of stools per day and looser than normal). Parents will be instructed not to take temperature after bundling and how to distinguish vomiting from normal spitting. Data will be collected using review of memory cards with the parent. We have found this to be accurate, simple and acceptable to the parents of young infants. The following reactogenicity signs/symptoms will be collected:

- Diarrhea: defined as 3 or more episodes of looser-than-normal stools in 1 day
- Vomiting: 1 episode of vomiting (forceful expulsion of partially digested milk/food) in 1 day
- Fever: axillary temperature  $\geq 99.5$  degrees F (measured once daily or more frequently if perceived fever)
- Hematochezia: maroon stools or any evidence of blood in the stool-black and tarry stools or frank red blood
- Irritability

The following grading system will be used in evaluating the fever and systemic events during Days1-14 following vaccination:

Reaction	Mild (Grade 1)	Moderate (Grade 2)	Severe (Grade 3)
Fever (axillary)	$\geq 99.5^{\circ}\text{F}$ to $\leq 100.4^{\circ}\text{F}$	$>100.4^{\circ}\text{F}$ to $\leq 102.2$	$>102.2^{\circ}\text{F}$ and higher
Diarrhea	3 looser than normal stools/ day	4-5 loose stools/ day	$> 6$ loose stools/ day
Vomiting	1 episode of vomiting/ day	2 episodes of vomiting/ day	$\geq 3$ episodes of vomiting/ day
Irritability	Crying more than usual	Some interference with normal activity	Significant interference with normal activity
Hematochezia	Any stools that are black and tarry; maroon in color; or, frank red blood-each episode will be reported to infant's medical provider immediately		

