## **7.3 Assessment of Subject Compliance With Study Product**

The study vaccines, RotaTeq® and Rotarix®, will be administered by the study product administrator, who is licensed to administer the vaccine (e.g., LPN [licensed practical nurse], RN [registered nurse], NP [nurse practitioner], PA [physician assistant], or medical doctor [MD]), in the clinic. Study personnel will record the administration time on the CRF and include whether it was a complete dose or a partial dose due to regurgitation.

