## **10 RANDOMIZATION, DATA MANAGEMENT, STATISTICAL PLAN**

### **10.1 Randomization Plan**

Upon meeting the inclusion and exclusion criteria, subjects will be randomized to one of the four vaccine groups: 1) RV1 alone, 2) RV5 alone, 3) RV1 with routine immunizations (DTaP, Hib, PCV13, HBV and IPV) or 4) RV5 with routine immunizations. This will be a simple randomization using SAS® PROC PLAN, which uses a random number generator to make assignments. Study statisticians will generate the assignments in advance of any enrollment. After obtaining informed consent, an unblinded research personnel will contact the statistician to obtain a specific subject's assignment. Parents and all study radiologists will be blinded as to which arm the child is randomized to until completion of the study. Parents will learn which rotavirus the child received at the completion of Visit 3. Parents will be informed about the specific other vaccines used in the study. If there is an urgent medical need to unblind during the study, then this can be done by calling the on call study staff.

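### Replacing infants who vomit within 15 minutes of vaccination selects the analysed infants on a post-randomisation event that is itself a reactogenicity outcome, and the analysis plan neither limits the rule nor restores them

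*Combined protocol and SAP*

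**What the plan says.** - **The rule.** Section 4.4, Reasons for Withdrawal, item 7: "infants who vomit within 15 minutes of rotavirus vaccination will not be withdrawn but will be replaced for analysis purposes". It stands in a list of reasons for withdrawal but states that these infants are not withdrawn.
- **Order of events.** Section 4.4, Randomization Procedures: "Randomization will take place prior to the vaccine administration". Sections 5.3 and 6.1 agree: infants are randomised before Visit 1 and vaccinated at that visit after imaging.
- **The event is an outcome.** Section 6.8 lists as a solicited event "Vomiting: 1 episode of vomiting (forceful expulsion of partially digested milk/food) in 1 day", which is Grade 1 in its table. Reactogenicity belongs to exploratory objective 2 (section 3.3).
- **The window.** Section 6.8: "Reactogenicity will be assessed for both groups for fourteen days after vaccine receipt (Days 0-14"). The sentence introducing the grading table in the same section starts at Day 1 instead.
- **What is recorded.** Visit 1 (section 5.3) documents the times of vaccination and of any vomiting, with no repeat dose. Section 7.3 records "whether it was a complete dose or a partial dose due to regurgitation".
- **Allocation.** "Infants will be randomized 1:1:1:1 to one of four groups" (section 4.4). Section 10.1: "This will be a simple randomization using SAS ® PROC PLAN, which uses a random number generator to make assignments". Neither says how a replacement infant is assigned.
- **Analysis plan.** Section 10.3 does not mention item 7, defines no analysis set and plans no sensitivity analysis for these infants.

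**The concern.** Randomisation makes the four arms comparable as randomised. If infants leave the analysis because of something that happened after the vaccine was given, the remaining infants are comparable only if that event is unrelated to arm and to outcome. Here the event is an outcome, so the relation to outcome is certain for vomiting. Replacing an infant removes the early episode and, with it, every later reactogenicity event in that infant.

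At stake is the reported frequency of vomiting after each vaccine, and any RV1 versus RV5 difference in it. The imaging comparison is exposed in principle too: early vomiting could be associated with gut function, which this trial studies. The section on power says that effect sizes will be reported to help design later studies, so readers need to know which infants those estimates describe.

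**Working it through.** The plan has no figure to reproduce: the section headed Power says the sample size was predetermined and no power calculation was made. All rates below are assumptions. The documents name vomiting as an anticipated common event for both vaccines (section 11.1, at least 5% for RV1) but give no rate within 15 minutes and no comparison between vaccines.

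**1. Effect on the reported vomiting rate.** Let v be the share of infants who vomit at any time in follow-up and s the share of those who do so within 15 minutes. If early vomiters are replaced by infants selected in the same way, the reported rate is (v − v·s)/(1 − v·s).

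| v | s = 20% | s = 50% |
|---|---|---|
| 5% | 0.040/0.990 = 4.0% | 0.025/0.975 = 2.6% |
| 10% | 0.080/0.980 = 8.2% | 0.050/0.950 = 5.3% |
| 15% | 0.120/0.970 = 12.4% | 0.075/0.925 = 8.1% |

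**2. Effect on a difference between arms.** Let p be the share vomiting early. Assume that 10% of the others vomit later in both arms. The true rate of any vomiting is p + (1 − p)·0.10.

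- Early 5% v 2%: 14.5% v 11.8%, a difference of 2.7 points.
- Early 10% v 2%: 19.0% v 11.8%, a difference of 7.2 points.

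After replacement both arms show 10%, and the difference is 0 in each case.

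**3. Effect on the primary outcome** (pre-post change in terminal ileum thickness). Let D be the difference in mean change, in SD units, between early vomiters and the rest, taken as equal in both arms. The between-arm contrast with early vomiters left out differs from that in all infants by (pA − pB)·D. With up to 150 infants in four arms, n = 37.5 per arm, and the standard error (SE) of a pairwise difference is √(2/37.5) = 0.231 SD.

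| Early vomiting | D | Bias (SD) | Share of SE |
|---|---|---|---|
| 2% v 1% | 0.25 | 0.0025 | about 1% |
| 5% v 2% | 0.5 | 0.015 | about 6% |
| 10% v 2% | 1.0 | 0.08 | about 35% |

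The last row needs both a large imbalance and a full SD of difference.

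**4. Number affected.** At early-vomiting rates of 1%, 2%, 5% or 10%, 150·p gives 1.5, 3, 7.5 or 15 infants replaced among 150. Keeping 150 in the analysis would need 150/(1 − p), rounded up: 152, 154, 158 or 167 infants. Sections 4.1 and 4.2 allow up to 150 and do not say whether replacements count towards that number.

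**The case against.** The strongest defence is that item 7 does not say which analyses it governs. Vomiting times are recorded, and section 10.3 promises descriptive statistics, reactogenicity included, for the whole study population as well as by group. The rule could therefore be meant only for imaging, cytokine and shedding analyses, where it matters whether the dose was retained. In an unpowered mechanistic pilot that is a legitimate question. If grading really starts on Day 1, an episode in the clinic on Day 0 may not reach the graded summary in any case.

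The ambiguity is real, so understated vomiting is a consequence of the ordinary reading and not a settled fact. But nothing in section 10.3 adopts the narrower reading. A Day 1 start would not protect the later events of a replaced infant. The dose-retained question can be kept as a sensitivity analysis.

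A reader might infer more than the documents support:

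- **That completion rates would look better.** These infants stay in the study and can meet the completion benchmark in Appendix 2. The general provision "Subjects who are withdrawn may be replaced if deemed necessary by the study team to meet study enrollment goals" concerns withdrawn infants and does not cover them. Whether they count in the feasibility denominators is simply unstated.
- **That the two vaccines differ in early vomiting.** The dose volumes differ (2 mL for RV5, 1 mL for RV1; section 7.2), but no text links volume to vomiting.
- **That the contrast feed drives the problem.** By section 6.6 the feed ends about 5 minutes before imaging. A scan of 30-60 minutes and an ultrasound of up to 30 minutes follow, so vaccination comes about 35 to 95 minutes after the feed. The feed is also the same in all arms.
- **That partial-dose infants are kept while early vomiters are dropped.** Sections 7.2 and 7.3 cover re-dosing and recording only and are silent on analysis.

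**Conclusion.** The point holds as a matter of design. As written, item 7 makes inclusion in the analysis depend on a post-randomisation, post-vaccination event that is also a solicited outcome, and section 10.3 neither limits it nor offsets it. The main exposure is the reactogenicity comparison. Under the assumed rates, reported vomiting falls by about 1 to 7 points (from 5% to 4.0% at the least, from 15% to 8.1% at the most), and a true difference of 2.7 or 7.2 points between arms would disappear.

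It would go too far to say that the primary comparison is seriously biased. In the two modest scenarios the shift is about 1% to 6% of the pairwise SE, and only an extreme scenario brings it to 35%. Every one of these figures rests on assumed rates, and unequal early vomiting between arms is a possibility that the documents do not demonstrate. The change is still worth making, because follow-up of these infants continues and the times are already recorded, so no new data are needed.

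**What to change.** 1. Reword item 7 so that early vomiters are not replaced in the analysis.
2. In section 10.3, define the main set for imaging and reactogenicity as all randomised and vaccinated infants with available data, in their assigned arm. Count vomiting on Day 0, and reconcile the two windows in section 6.8 (Days 0-14 and Days 1-14).
3. Report the number of infants vomiting within 15 minutes by arm.
4. For feasibility, use all enrolled or randomised infants, as each benchmark requires. A vaccinated-only denominator would omit infants who never attended Visit 1 or failed the first MRI, and so would flatter feasibility.
5. Present a dose-retained set (no vomiting within 15 minutes, complete dose) as a sensitivity analysis for imaging, shedding and cytokines.
6. State that extra infants may be enrolled from the same randomisation list but replace no one.

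The cost is wording, one sensitivity analysis, and slight dilution of any vaccine effect by infants who lost part of the dose. Nothing here proposes a dosing or clinical rule.

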##### **Handling of Withdrawals**

Every effort will be made to undertake protocol-specific safety follow-up procedures for subjects who are withdrawn by their parents/legal guardians. The subject's parents/legal guardians will be encouraged to participate in the final follow-up contact to occur 14 days after the initial visit.

Subjects who are withdrawn may be replaced if deemed necessary by the study team to meet study enrollment goals.

## **5 STUDY SCHEDULE ( See Appendix 1)**

### **5.1 Recruitment and Enrollment**

Recruitment will be done by our study personnel through the Pediatric Primary Care (PPC) Clinic at CCHMC and through study advertisement at CCHMC targeted towards our employee e-mail system and database of past research participants who have agreed to be e-mailed for future studies. Any written communication provided to the potential subjects' parents/legal guardians about the study will be submitted to the IRB for their approval before study initiation.

We routinely conduct studies through the PPC and our research personnel are present in the clinic. We will review the patients scheduled and will identify those who are age eligible for the study. The medical

record for those age-eligible will be screened to identify children who would not be eligible for the study (exclusion criteria). Parents of potentially eligible infants will be approached to discuss participation in the study. If interested, informed consent will be obtained before giving instructions and scheduling Visit 1. After consent is obtained, infant will be randomized into one of four study groups.

For recruitment of infants of CCHMC employees and through our research database, the interested parent will call our study line. Relatives of study personnel will be excluded from participation as is standard procedure. Study personnel will discuss the study by phone. Subjects will be screened by medical history from the parent. If eligible and interested, a meeting time will be arranged prior to Visit 1 to obtain informed consent. The infant's primary care provider will be contacted to determine if the infant is healthy and to inform the primary care provider of the study after informed consent and prior to Visit 1. Parents will be informed that their decision to participate or not to participate in the study will not have any effect on them as an employee.

Because the infants to be enrolled will be healthy and will be receiving a licensed vaccine that is approved for use in this population, no additional screening will be necessary. No baseline laboratory screening will be performed prior to enrollment. Screening records will be kept to document the reason why a subject was screened but failed entrance criteria. If a parent chooses not to agree to the study, we will ask for a reason and it will be documented.

Infants must be 6 weeks to 13 weeks of age (12 weeks, 6 days) for Visit 1, the day of immunization. Inclusion and exclusion criteria will be reviewed. All medications taken within the 30 days prior to enrollment will be recorded. Demographic and contact information will be obtained. The parent/legal guardian will be given containers for stool and breast milk collection at home. Instructions will be given to the parent with the date, time and location for Visit 1 and the need for their infant to be NPO for 3 hours prior to appointment and to return with a stool collected the day of Visit 1 (note for MRI must be 4 hours NPO, but will ask to be 3 hours NPO since it will take ~one hour from arrival until feed for MRI).

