## 5.3 Study Visits

### Enrollment/Recruitment Visit

- review inclusion/exclusion criteria and medical history
- obtain informed consent
- obtain a release to get medical information from the primary care provider
- collect contact information including the primary care provider of infant and the date of 2 month check up if known
- if refuses study, record refusal reason on screening log
- sample collection instructions
- distribute sample collection supplies
- review MRI and ultrasound prep
- randomize to study group and inform parent of result of all routine vaccines or rotavirus vaccine alone (not specific rotavirus vaccine type)
- schedule visit 1  
give written instructions for Visit 1 to parent (Appendix 5) **Reminder Call 1 (day prior to Visit 1)**
- review sample collection instructions
- review MRI/ultrasound prep  
review time, date and location of Visit 1 **Visit 1 (Day 0-Vaccine Administration)**
- contact information will be reviewed and updated if necessary
- inclusion and exclusion criteria will be reviewed to determine if child still meets criteria for study
- temperature will be recorded prior to immunization; axillary temperature must be <100.4° F prior to administration of vaccines
- breast milk specimen brought from home if mother is breast feeding or can be collected at the visit if needed
- saliva specimen collected for human blood group antigen testing
- baseline stool specimen (brought from home) before receiving the rotavirus vaccine
- MRI to assess intestinal anatomy and motility
- Ultrasound of abdomen to assess intestinal anatomy
- baseline blood specimen for cytokine testing and maternal antibody testing (IgG)
- The Vaccine Information Sheet (VIS) will be provided to parents/guardians for all vaccines administered.
- The study product administrator, who is licensed to administer the vaccine (e.g., MA, LPN, RN, NP, PA, or MD), will orally administer the rotavirus vaccine as indicated in the randomization code
  - if the infant vomits after receiving the vaccine, in accordance with AAP and ACIP recommendations, the vaccine will not be readministered but time of vaccine administration and vomiting will both be documented.

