## 6 STUDY PROCEDURES

### 6.1 Rotavirus Vaccine Randomization and Administration

Infants will be randomized to receive 1) RV1 alone, 2) RV5 alone, 3) RV1 with routine immunizations (DTaP, Hib, PCV13, HBV and IPV or 4) RV5 with routine immunizations prior to Visit 1. They will receive the vaccination(s) after the MRI/Ultrasound is completed at Visit 1.

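### The arm is drawn at enrolment, although sections 4.4 and 10.1 require eligibility first and some criteria can be judged only at Visit 1; exclusions after randomisation could therefore differ by arm

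*Combined protocol and SAP*

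**What the plan says.** The protocol gives two rules for when the arm is drawn.

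**At enrolment.** Section 5.1: "After consent is obtained, infant will be randomized into one of four study groups". The enrolment list in section 5.3 includes the step "randomize to study group and inform parent of result of all routine vaccines or rotavirus vaccine alone (not specific rotavirus vaccine type", placed before Visit 1 is scheduled. Section 6.1 describes allocation to the four groups, ending "RV5 with routine immunizations prior to Visit 1".

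**After eligibility is established.** Section 4.4 allows the draw only once the parent has "signed the IRB-approved consent form and met all of the inclusion and none of the exclusion criteria". Section 10.1: "Upon meeting the inclusion and exclusion criteria, subjects will be randomized to one of the four vaccine groups".

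Appendix 1 marks the randomisation row at both enrolment and Day 0. The Visit 1 list in section 5.3 then states that "inclusion and exclusion criteria will be reviewed to determine if child still meets criteria for study".

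**The concern.** Staff cannot follow both rules. Under the enrolment rule, an infant already assigned to an arm can still be found ineligible at Visit 1. Exclusion after randomisation is harmless to the comparison only if it is unrelated to the arm, and two features of the plan leave that open. Parents know from enrolment whether routine vaccines will be given, and unblinded staff can know the rotavirus product before eligibility is re-judged.

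The between-group comparison of change in terminal ileum thickness (section 10.3) would then be made among infants selected partly after allocation. Section 10.3 defines no analysis set for infants who were randomised but found ineligible, not vaccinated or not scanned. Section 4.4 offers only discretionary replacement.

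**Working it through.** The plan has no figure to reproduce: section 10.3 says no power calculation was done, and it gives no dropout rate. The check is mainly a comparison of sections.

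**1. Can all criteria be met at enrolment?** No.
- Vomiting and diarrhoea (4.3, exclusion 9): the windows run back from Visit 1, "within 24 hours prior to Visit 1 and/or diarrhea (3 watery stools) within 14 days of Visit 1".
- Antipyretics (exclusion 12): 72 hours before the first rotavirus dose.
- Fasting (exclusion 2): 4 hours before the MRI.
- Temperature (5.3): below 100.4° F at Visit 1, before vaccination.
- Physician confirmation (inclusion 2): due only by Visit 1. For the employee and database route, section 5.1 places this contact after consent.
- Age on vaccination day (inclusion 1) and 28 days since HBV (exclusion 3): these can be forecast from a booked date but are fixed only when the visit takes place.

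**2. Can a whole look-back window fall after the draw?** Yes. Appendix 1 recruits below 11 weeks of age and allows Visit 1 up to 12 weeks 6 days. For an infant enrolled at 10 weeks 6 days the longest gap is (12×7 + 6) − (10×7 + 6) = 90 − 76 = 14 days, which is the full diarrhoea window. Infants enrolled younger can have a longer gap, and no maximum is stated.

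**3. Who can know the arm at the re-check?** Parents know the routine-vaccine part (5.3). Under section 10.1, unblinded personnel obtain the assignment after consent. Blinding is stated only for parents and imaging staff (4.1, 10.1). Nothing says that the re-check, which includes the investigator-judgement criterion (exclusion 14), is made by staff unaware of the product.

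**4. Is there an arm-specific route to exclusion?** Yes. Section 5.2 tells families in the rotavirus-alone arms that routine vaccines may come two weeks or more before the rotavirus dose. Exclusion 3 permits only the initial HBV. An infant who followed that option would fail the Visit 1 re-check. Families in the other two arms are asked not to have the 2-month vaccines at the check-up. Section 5.2 and exclusion 3 must be reconciled.

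**5. How large is the loss?** Unknown. Appendix 2 would accept 30% of subjects not completing both MRIs (0.30 × 150 = 45), but that includes Visit 2 failures and is not a rate of loss before vaccination. As an illustration only, assume a loss L, 150 × (1 − L)/4 infants per arm, and one pairwise two-sample t-test at two-sided 5% with 80% power:

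| Assumed L | Infants lost of 150 | Per arm | Detectable difference |
|---|---|---|---|
| 0% | 0 | 37.5 | 0.66 SD |
| 10% | 15 | 33.8 | 0.69 SD |
| 20% | 30 | 30.0 | 0.74 SD |

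An infant who is ill or absent at Visit 1 provides no pair of scans whenever the arm is drawn. The table therefore shows the cost of loss in general, not the cost of drawing early.

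**6. What does a split draw protect?** Section 10.1 specifies simple randomisation. Two independent 1:1 draws give each arm 1/2 × 1/2 = 1/4, so the 1:1:1:1 ratio is kept. Four groups give six pairwise comparisons (10.3):
- Two compare RV1 with RV5 at the same routine-vaccine status. With the product drawn after the re-check and baseline imaging, earlier losses cannot depend on it.
- Four involve the routine-vaccine factor and keep their present exposure.

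**The case against.** Early assignment is deliberate. Section 5.2 explains that families need to plan, the paediatrician receives a letter, and infants in the with-routine arms are asked to defer their 2-month vaccines. Sections 5.1 and 5.3 can be read as a two-stage check, at enrolment and again at Visit 1. Parents and imaging staff do not know the product, so loss before vaccination has no obvious reason to differ by RV1 or RV5. The route to differential loss is clearer for the routine-vaccine factor, and a split draw leaves that factor where it is. On this view only the wording needs alignment.

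Much of this stands. The planning reason is sound for the routine-vaccine factor, and reporting losses by that factor does not remove them. But the planning reason does not extend to the product, which parents are not told, and the plan does not keep the product from those who re-judge eligibility.

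Stronger readings that a reader might infer are not supported:
- **A known loss of 15 to 30 infants.** This is an assumed 10–20% multiplied by 150. Several criteria are transient, and the documents do not say whether Visit 1 may be rescheduled.
- **A gain in evaluable infants from a later draw.** The number evaluable per number enrolled does not change.
- **A serious cost from used assignments.** Randomisation is simple, with no blocks or strata stated, and section 4.4 allows replacement. A replacement need not enter the arm that lost an infant, but wasted assignments are a minor matter.
- **A failed baseline MRI as ineligibility.** No criterion requires a successful scan. A failed scan is missing outcome data, and MRI completion is itself a feasibility benchmark in Appendix 2.

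**Conclusion.** The point holds as a contradiction about timing with a consequence for bias. Sections 5.1, 5.3 and 6.1 cannot be reconciled with 4.4 and 10.1, and Appendix 1 supports both. Because some criteria can be settled only at Visit 1, the enrolment rule means that eligibility is re-judged after the draw while parents know one factor and unblinded staff can know the other.

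The possible harm is exclusion that differs by arm. The documents do not show that it would occur, and give no rate from which to size it. The conclusion rests on the timing text and on the absence of any statement that the re-check is masked to product; it does not rest on an assumed loss. The plan should be changed, but in a pilot without a power target this does not undermine the trial.

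**What to change.** - Keep the draw for with or without routine vaccines at enrolment, and give the planning reason from section 5.2.
- Have unblinded staff obtain the RV1/RV5 assignment from the statistician at Visit 1, after the eligibility re-check and baseline imaging and before vaccination. Section 6.1 already places vaccination after imaging.
- Amend 4.4 and 10.1 as well as 5.1, 5.3, 6.1 and Appendix 1 to state this two-step timing. Sections 4.4 and 10.1 must be included, because the enrolment draw would otherwise still breach them.
- Report losses between enrolment and vaccination by routine-vaccine allocation, and state in section 10.3 how these infants are handled. Acknowledge there that the routine-vaccine comparison remains exposed to loss before Visit 1 and that Visit 2 losses are unaffected.

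The cost is revised wording, a second assignment list prepared in advance, and a second allocation call on an already busy Visit 1.
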